10.2. Pharmacodynamic and Biomarker Analyses

Not applicable.

11. SAFETY AND TOLERABILITY ANALYSES

Tables in this section will present summaries by cohort unless otherwise specified.

11.1. Adverse Events

AEs will be assessed and recorded from the time of signing of the informed consent through the last follow-up visit or until the AE is resolved or the subject is in a clinically stable condition with regards to the AE. AEs will be assigned as pre-treatment, treatment-emergent, or post-treatment according to the start date of the event. Events occurring prior to the start of study drug (ie, berotralstat) will be considered pretreatment and any AE reported as related to treatment will be attributed to SOC treatment and not berotralstat. Events starting on or after the initiation of study drug (ie, berotralstat) in Part 1 will be considered treatment-emergent or post-treatment and any AE reported as related to treatment during these periods will be assigned to berotralstat.

AEs will be mapped to system organ classification and PT using MedDRA version 25.0. Relationship to study drug will be assessed as not related or related. AEs will be graded according to the DAIDS table for grading the severity of adult and pediatric AEs (Publish date July 2017, see Protocol Appendix Section 15.1). AEs not covered by the DAIDS table will be assessed and classified into 1 of 5 severity categories: mild, moderate, severe, life-threatening, and death, corresponding to toxicity Grades 1 through 5. Should an event have a missing relationship or severity, these events will be classified as 'related' or 'severe'.

The duration of AEs in days will be derived and presented in all listings; this value is calculated as (AE stop date/time – AE start date/time). Both start and stop dates must be present to calculate a duration. Duration will not be calculated if either the start or stop date is imputed.

No events of special interest have been identified in this protocol.

TEAEs are defined as AEs that occurred on or after first dose of berotralstat through 30 days post discontinuation of study treatment. All AEs that occurred prior to the initiation of berotralstat or those recorded after 30 days after the last dose of berotralstat will be excluded from the tables but will be included in the listings. All AEs will be listed for individual subjects showing both verbatim and preferred terms.

An overall summary of AEs will be produced to summarize the number and percentage of subjects reporting:

- Any TEAE
- Any treatment-emergent SAE (TESAE)
- Any drug related TEAE
- Any drug related TESAE

- Any Grade 3 or Grade 4 TEAE
- Any drug-related Grade 3 or Grade 4 TEAE
- Any TEAE leading to interruption of study drug (berotralstat)
- Any TEAE leading to discontinuation of study drug (berotralstat)
- Any TEAE leading to death.

TEAEs will be summarized by system organ class, PT, and cohort. TEAEs will also be summarized by system organ class, PT, severity, and cohort. TEAEs considered to be related to study drug will be summarized by system organ class, PT, and cohort. TESAEs will be summarized by system organ class, PT, and cohort. In addition, tables and listings of subjects who reported a TEAE with a preferred term that is included in the Hypersensitivity (narrow terms), Anaphylactic Reaction (narrow and broad terms) or Severe Cutaneous Reactions (narrow terms) standardized MedDRA queries (SMQs) will be generated. In addition, a table and listing will be generated for subjects who report either a TEAE with a preferred term that is included in the Torsade de Pointes (TdP)/QT prolongation SMQ or a TEAE with the preferred term Palpitation.

AEs, SAEs, and TEAEs considered to be related to study drug will be listed separately by treatment group, cohort, subject, and start date, showing system organ class, PT, and verbatim term.

An overall summary of AEs reported in the SOC period will be produced to summarize the overall number and percentage of subjects reporting:

- Any AE
- Any SAE
- Any drug related AE
- Any Grade 3 or Grade 4 AE
- Any AE leading to death.

A summary table of AEs reported in the SOC period will be presented overall by system organ class and PT. All AEs reported during the SOC will be listed.

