11.1.1.4. Definition of Severity

All AEs and SAEs will be assessed (graded) for severity by the investigator and classified using the Division of AIDS (DAIDS) table for grading the severity of adult and pediatric AEs (Publish date July 2017). Any AEs not covered by the DAIDS table will be assessed and classified into 1 of 5 clearly defined categories as follows:

- Mild:** (Grade 1): Mild symptoms causing no or minimal interference with usual social & functional activities with intervention not indicated.
- Moderate:** (Grade 2): Moderate symptoms causing greater than minimal interference with usual social & functional activities with intervention indicated.

Severe: (Grade 3): Severe symptoms causing inability to perform usual social & functional activities with intervention or hospitalization indicated.

Life-threatening: (Grade 4): Potentially life-threatening symptoms causing inability to perform basic self-care functions with intervention indicated to prevent permanent impairment, persistent disability, or death.

Death: (Grade 5): Indicates death related to the AE.

The investigator should report the highest severity experienced during the course of the event. It is important to distinguish between serious and severe AEs. Severity is a measure of intensity, defined above, whereas seriousness is defined by the criteria under Section 11.1.1.4. An AE of severe intensity may or may not be considered serious. An example would be a severe headache that does not result in any serious outcome is a non-serious AE; conversely, a mild event that results in hospitalization is a serious AE.

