11.1.1.5. Definition of Relationship to Study Drug

Using the following guidelines, an investigator who is qualified in medicine must make the determination of relationship to berotralstat or SOC HAE medication used for prophylaxis and/or acute therapy for each AE (not related or related). The investigator should decide whether, in his or her medical judgment, there is a reasonable possibility that the event may have been caused by berotralstat or SOC HAE medication. If no valid reason exists for suggesting a relationship, then the AE should be classified as “not related.” If there is any valid reason, even if undetermined, for suspecting a possible cause-and-effect relationship between berotralstat or SOC HAE medication and the occurrence of the AE, then the AE should be considered “related.”

Because multiple study drugs are being administered in this study, the investigator should assess causality individually to berotralstat or SOC HAE medication, taking into consideration the timing of the AEs in relation to berotralstat or SOC HAE medication dosing as well as the known safety profile of berotralstat or SOC HAE medication.

The degree of certainty with which an AE is attributed to berotralstat or SOC HAE medication (or alternative causes, eg, natural history of the underlying disease, concomitant therapy) will be determined by how well the experience can be understood in terms of one or more of the following:

- Known pharmacology of berotralstat or SOC HAE medication
- Reactions of a similar nature have been previously observed with berotralstat or SOC HAE or these classes of drugs
- The experience being related by time to berotralstat or SOC HAE medication, terminating with their withdrawal or recurring on re-challenge
- Alternative cause

The investigator should assess causality by determining whether the AE/SAE is suspected to be caused by the investigational product based on facts, evidence, science-based rationales, and clinical judgement as follows:

- Not Related:** The temporal relationship of the AE/SAE to investigational product administration makes a causal relationship unlikely, OR other drugs, therapeutic interventions or underlying conditions provide a sufficient explanation for the AE/SAE.

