6.7.4. Treatment-Emergent Adverse Events

TEAEs are defined as AEs that occurred on or after first dose of study treatment through 30 days post-discontinuation of study treatment. Additionally, it is assumed that an AE which was reported to have started on Day 1 without an associated onset time may have occurred after the initiation of berotralstat. Hence, AEs occurring on Day 1 with no associated onset time will be assumed to be treatment emergent.

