8.5.2. Missing Start and Stop Dates for Prior and Concomitant Medication

For analysis of medications, a complete date should be established to identify whether a medication was taken during the study treatment period or not. The following algorithm will be applied to handle partially reported start and stop dates for medications:

- Missing start day, but month and year present:

If study medication had been taken in the same month and year as the occurrence of the medication, then the start day of the event/medication will be assigned to the day of first dose of study medication.

Otherwise, the start day will be set to the first day of the month.

- Missing start day and month, but year present:

If study medication had been taken in the same year as the occurrence of the medication, then the start date of the medication will be assigned to the date of first dose of study medication.

Otherwise, the start day and month will be set to 01 January.

- Missing end day, but month and year present:

The day will be set to the last day of the month.

- Missing end day and month, but year present:

The end day and month will be set to the date of study termination.

However, if study termination year is greater than the year of the event/medication, then the day and month will be set to 31 December.

- Completely missing start date:

For HAE medications collected on subject diaries, the date will be set to the corresponding HAE attack date. For all other concomitant medications, a completely missing start date will be set to the treatment start date (if prior to the medication end date) or otherwise will be set to the medication end date.

In subject data listings, start and stop date of medication will be displayed as reported on the eCRF.

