8.5.3. Missing Start and Stop Dates for Adverse Events

The same conventions for addressing incomplete dates for prior and concomitant medications will also be used for AEs.

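### AE rules in the SAP can misclassify relatedness, treatment emergence and study part in the descriptive safety tables

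*SAP*

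**What the plan says.** **Attribution.** SAP 11.1 sorts events by calendar: "AEs will be assigned as pre-treatment, treatment-emergent, or post-treatment according to the start date of the event". For related events before the first dose, "any AE reported as related to treatment will be attributed to SOC treatment and not berotralstat". From the first dose onward, "any AE reported as related to treatment during these periods will be assigned to berotralstat". Protocol 11.1.1.5 instead asks for a judgement by drug: "the investigator should assess causality individually to berotralstat or SOC HAE medication". It makes clear that SOC HAE medication covers acute therapy as well as prophylaxis. Both documents let on-demand treatment continue for the whole study.

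**Treatment emergence.** SAP 6.7.4: "TEAEs are defined as AEs that occurred on or after first dose of study treatment through 30 days post-discontinuation of study treatment". SAP 11.1 repeats this and leaves AEs with onset before the first dose out of the TEAE tables. On grading, Protocol 11.1.1.4 says: "The investigator should report the highest severity experienced during the course of the event".

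**Partial dates.** SAP 8.5.3: "The same conventions for addressing incomplete dates for prior and concomitant medications will also be used for AEs". When only the year is known, the medication rule in SAP 8.5.2 begins "If study medication had been taken in the same year as the occurrence of the medication, then the start date of the medication" and sets that date to the date of first dose. When only the day is missing, the same test is applied to the month and year.

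**The concern.** Safety is a secondary objective and its analysis is entirely descriptive, so the AE tables are the safety result. The interim analysis after at least 15 children complete 48 weeks is meant to support the NDA. Three tabulation rules, followed as written, can put an event in the wrong place:

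- (a) a reaction to an on-demand drug may appear in a table of berotralstat-related events;
- (b) a clinical event that becomes worse on berotralstat may be missing from the TEAE tables and appear in the SOC period at a grade reached on berotralstat;
- (c) an event with an incomplete start date may be placed in the wrong study part, or counted as a TEAE although it had resolved before dosing.

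The errors do not run in one direction. Rule (a) tends to overstate events related to berotralstat. Rule (b) tends to understate TEAEs and to raise severity in the period that Protocol 4.4.4 describes as a safety control.

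**Working it through.** **The plan's own figure.** Protocol 12.1 and SAP 4.7 give about a 96% chance of seeing at least one TEAE with a 10% rate among 30 children. 1 − (1 − 0.10)^30 = 1 − 0.9^30 = 0.9576, so the figure reproduces. It presumes that every child with the event is counted. If a share m of those children were missed, the chance would be 1 − (1 − 0.10 × (1 − m))^30:

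| Assumed share missed, m | Chance of at least one |
|---|---|
| 0 | 95.8% |
| 10% | 94.1% |
| 25% | 90.4% |
| 50% | 78.5% |

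The values of m are assumptions for illustration; the documents give no basis for choosing one.

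**(a) Attribution.** The protocol's judgement has two parts, one for each source of drug. SAP 11.1 describes a single related/not related item and allocates it by start date. The paired sentence sending related SOC-period events to SOC treatment would make little sense if that item concerned berotralstat only, so the item reads as generic. On that reading, a reaction to an on-demand drug in Parts 1 to 3 enters the drug-related tables (14.3.1.4, 14.3.1.6 and 14.3.1.8, all marked for the NDA interim). Table 7 has no output that separates such events. Only the relatedness label changes; the event is a TEAE either way.

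**(b) Worsening.** Take an AE that starts in the SOC period at Grade 1, is ongoing at Day 1 and reaches Grade 3 on berotralstat.

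1. Its start date precedes the first dose, so it is pre-treatment and outside the TEAE tables.
2. One highest grade is kept for the event, here Grade 3.
3. The SOC summary in SAP 11.1 has a line for Grade 3 or 4 AEs, so the event is counted there at a grade first reached on berotralstat.

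For laboratory data the SAP does handle this: 6.7.6 treats a rise of at least one grade from baseline as treatment-emergent. The gap is confined to clinical AEs kept on one record.

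**(c) Partial dates.** The rule tests whether study drug was being taken in the reported month or year, not whether the first dose fell in it.

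- *Year only.* Full dosing lasts 144 × 7 = 1,008 days, about 2.8 years, so it touches at least three calendar years. An AE known only to have started in the second or third of these meets the test and is moved to the first-dose date, against its own reported year. It would be a TEAE at either date, but it now falls in Part 1, which has separate tables (14.3.1.1.2 and 14.3.1.5.2).
- *Day missing, first-dose month.* Let the first dose be on day d, and let the AE stop on day s of the same month, with s < d. The start is set to d, which is after the stop date, and the AE becomes a TEAE although it ended before dosing. SAP 8.5.2 checks the end date only when the start date is completely missing.

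**Weight of one child.** With 30 enrolled, 1/30 = 3.3 percentage points. At the minimum cohort sizes in SAP Synopsis and Protocol Table 1, 1/4 = 25 points (Cohorts 1 to 3) and 1/3 = 33 points (Cohort 4).

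**The case against.** The case against a stronger conclusion is substantial, and most of it stands.

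- *On-demand reactions will be reported as berotralstat-related.* A reader might infer this, but it depends on the AE form, which is not in the documents. The category definitions in Protocol 11.1.1.5 refer to the investigational product and class an event as not related where another drug explains it sufficiently. If sites apply those definitions to berotralstat alone, an on-demand reaction never reaches the drug-related tables. The same section still demands a separate SOC judgement, and the SAP's wording does not say which item it uses. The conflict is real; its effect is conditional.
- *Worsening events are never counted.* This goes too far. Protocol 11.1.1.1 counts events that worsen, including worsened pre-existing conditions, as AEs, so a site could open a new record at worsening, and that record would be a TEAE. Nothing supplied requires this for an AE that began on study, and the highest-severity rule points to a single record. Laboratory worsening is captured, and SAP 11.5 categorises QTcF increases regardless of AE records.
- *The SOC-versus-berotralstat comparison is biased.* No such comparison is formally planned. SOC-period AEs are summarised separately, no hypothesis is tested, and 12 weeks against up to 144 weeks makes raw incidences unlike in any case.
- *Late partial-date events inflate the TEAE count.* They do not: an on-treatment event is a TEAE at its true date too. Duration is also protected, since SAP 11.1 does not calculate it from an imputed date.
- *25 to 33 points measures the error.* It is the weight of any one child in a cohort of minimum size, not an estimate of how often the rules go wrong.

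Finally, all AEs are listed individually, and with about 30 children a case-by-case review is feasible. That limits the harm, but it does not correct the summary tables.

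**Conclusion.** The concern holds in a limited form. SAP 11.1, 6.7.4 and 8.5.2 to 8.5.3 state rules that can give wrong tabulations when followed.

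- (a) can overstate drug-related TEAEs, on the assumption that the AE form yields a generic relatedness item or that the SAP pools the two items; total TEAE counts do not change.
- (b) leaves a clinical AE that worsens after Day 1 in the SOC summary, possibly at its on-treatment grade, on the assumption that the site does not open a new record.
- (c) needs no assumption about the form, but affects only AEs with incomplete start dates: year-only events can move into the Part 1 tables, and an event that resolved before dosing can become a TEAE.

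How many events are affected cannot be derived from the documents. The primary PK endpoint and every inferential statement are untouched, there being none of the latter. This should be fixed before the safety tables are produced; it does not undermine the study.

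**What to change.** - (a) Define drug-related TEAEs by the investigator's berotralstat-specific causality, and list or tabulate events related to SOC or on-demand medication separately. If the AE form holds only one relatedness item, it needs the second that the protocol already calls for.
- (b) Define a TEAE as an AE with onset on or after the first dose, or with an increase in grade after it. Instruct sites to record worsening after the first dose as a new AE, so that the SOC-period summary carries the pre-dose grade. This has to be aligned with the highest-severity rule in Protocol 11.1.1.4.
- (c) Impute a start to the first-dose date only when the reported month and year (or the year, if that is all that is known) match those of the first dose, and never later than the reported stop date.

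Cost: SAP wording, a CRF completion instruction and a small protocol alignment. TEAE counts may rise slightly through worsening events.
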